8.2.2 Glycemic

All of following metrics will be generated from the Dexcom G4 Platinum CGM data during each treatment visit:

- Fraction of time spent within each of the following glucose ranges:
 - <50 mg/dL
 - <60 mg/dL
 - <70 mg/dL
 - 70-120 mg/dL
 - 70-140 mg/dL
 - 70-180 mg/dL
 - >180 mg/dL
 - >250 mg/dL
 - >300 mg/dL
- Number of severe hypoglycemic events (patients unable to self-treat, requiring the assistance of another person)
- Number of episodes of symptomatic hypoglycemia
- Number of carbohydrate interventions for hypoglycemia
- Total grams of carbohydrates taken for hypoglycemia
- Mean CGM glucose

8.2.3 Non-glycemic

- Glucagon/ZP4207 total delivery per kg of body mass
- Insulin total delivery per kg of body mass
- Number of unscheduled infusion set replacements
- Number of unscheduled CGM sensor changes

9 LABORATORY ASSESSMENTS

Descriptions of sample handling and sample processing, storage, and shipment at the site will be included in the laboratory manual.

The responsible laboratories are listed in the [address list](#).

9.1 Safety Laboratory Assessments

Chemistry and hematology samples will be collected at specified time points. See [Appendix A](#) for the schedule of procedures and [Appendix B](#) for a list of clinical laboratory analytes.

9.2 Pharmacodynamic Assessments (Plasma Glucose)

At Visit 3 and Visit 4, plasma glucose samples will be taken from the IV at least hourly in parallel with ZP4207/glucagon exposure sampling and measured using the YSI 2300 STAT Plus. If the YSI 2300 STAT Plus and/or IV fails, the Nova StatStrip Xpress will be used for glucose measurements. If BG is <150 mg/dL, then sampling will be every 30 minutes. If BG is

Clinical Trial Protocol
ZP4207-16051

Version number: 8.0
Amendment 7.0
Date: 06 January 2017

<100 mg/dL, then sampling will be every 20 minutes. If BG is <80 mg/dL, then sampling will be every 10 minutes. The actual time of sampling will be recorded in the eCRF.

9.3 Exposure Assessments (ZP4207 and Glucagon)

At Visit 3 and Visit 4, ZP4207/glucagon exposure sampling will be collected at least hourly. If BG is <150 mg/dL, more frequent samples for plasma ZP4207/glucagon may be drawn at the discretion of the Investigator. The actual time of sampling will be recorded in the eCRF.

Bioanalytical Reports will be prepared.

9.4 Anti-drug Antibodies Assessments

Blood samples (including back-up samples) for serum anti-ZP4207 and anti-glucagon antibodies will be taken at Visit 3, the ADA Assessment Visit (Visit 5), and the Follow-up Visit (Visit 6). Any patient that tests positive for ADA will be monitored until the ADA levels return to baseline.

Bioanalytical Reports will be prepared.

10 SAFETY REPORTING

10.1 Adverse Events

An AE is any untoward medical occurrence in a trial patient administered an IMP and which does not necessarily have a causal relationship with the treatment. An AE can therefore be any unfavorable and unintended sign (e.g., an abnormal laboratory finding), symptom, or disease temporally associated with the use of an IMP, whether or not considered related to the IMP. Patients should be instructed to report any AE they experience to the Investigator. Note: This includes events from the first trial-related activity from Visit 3.

AEs for ZP4207 include:

- A clinically significant worsening of a concomitant illness
- A clinical laboratory abnormality which is clinically significant, i.e., any abnormality that suggests a disease and/or organ toxicity and is of a severity that requires active management. Active management includes active treatment or further investigations, for example, change of medicine dose or more frequent follow-up due to the abnormality.
- Hypoglycemic episodes
- Injection site reactions

The following should **not** be recorded as AEs, if recorded prior to randomization (on the Screening Form or the eCRF):

- Pre-planned procedure, unless the condition for which the procedure was planned has worsened from the first trial-related activity from Visit 3.
- Pre-existing conditions found as a result of screening procedures (pre-existing conditions should be reported as medical history or concomitant illness).

For known (listed) AEs for Glucagon and Humalog, please refer to SPC for [Glucagon](#) and [Humalog](#).

Clinical Trial Protocol
ZP4207-16051

Version number: 8.0
Amendment 7.0
Date: 06 January 2017

10.1.1 Follow-up of Adverse Events

All AEs that are ongoing at the end of the patient's participation in the trial will be followed-up until the event is resolved or reaches a satisfactory outcome as deemed by the Investigator. Follow-up actions for all serious adverse events (SAEs) will be performed according to appropriate clinical care practices and may depend on the nature of the event. These will be determined after internal review and/or Sponsor review. The follow-up information should only include new (updated and/or additional) information that reflects the situation at the time of the Investigator's signature.

Follow-up information on (S)AEs will be updated using the (S)AE Form. If a non-serious event becomes serious during the follow-up, the AE Form and SAE Form must be used and reporting timelines follow those of an SAE.

The Investigator must forward follow-up information on SAEs, and if previously non-serious AEs become SAEs, to the Sponsor.

10.1.2 Precautions

Normal precautions taken for a human trial will be taken during this trial. Qualified and well-trained physicians and medical staff will instruct the patients. During a patient's participation in the trial, the Investigator should ensure that adequate medical care is provided to the patient for any AEs, including clinically significant laboratory values related to the trial. The Investigator should inform the patient when medical care is needed for intercurrent illnesses of which the Investigator becomes aware.

For further information on safety precautions for ZP4207, Lilly glucagon, and Lilly Humalog, please refer to the current version of the Investigator's Brochure (IB) for ZP4207 ([Zealand Pharma A/S, 2015](#), or any updates hereof), and the SPC for Glucagon ([Eli Lilly, 2012](#)) and Humalog ([Eli Lilly, 2015](#)), respectively.

10.1.3 Assessment of Adverse Events by the Investigator

Intensity of an Adverse Event

The maximum intensity (severity) of all AEs must be assessed by the Investigator and documented. Severity should be graded when the AE outcome is known:

- **Mild:** A type of AE that is usually transient and may require only minimal treatment or therapeutic intervention. The event does not generally interfere with usual activities of daily living.
- **Moderate:** A type of AE that is usually alleviated with additional specific therapeutic intervention. The event interferes with usual activities of daily living, causing discomfort but poses no significant or permanent risk of harm to the patient.
- **Severe:** A type of AE that interrupts usual activities of daily living, or significantly affects clinical status, or may require intensive therapeutic intervention.

A "severe" reaction does not necessarily deem the AE as "serious," and an SAE may not be "severe" in nature.

Clinical Trial Protocol
ZP4207-16051

Version number: 8.0
Amendment 7.0
Date: 06 January 2017

Causality Relationship to IMP

Insulin (insulin lispro, Lilly Humalog), glucagon (glucagon for injection, Eli Lilly), and ZP4207 are all regarded as IMP.

The causality of each AE should be assessed by the Investigator according to the following classification:

- Related: Good reason and sufficient documentation to assume a causal relationship.
- Not related: No relationship to trial product can be established.

Outcome of an Adverse Event

The outcome of all AEs must be assessed by the Investigator and documented by his/her staff. The following definitions should be used:

- Recovered/resolved: The patient has fully recovered, or by medical or surgical treatment the condition has returned to the level observed at the first trial-related activity from Visit 3.
- Recovering/resolving: The condition is improving and the patient is expected to recover from the event. This term is only applicable if the patient has completed the trial.
- Recovered/resolved with sequelae: The patient has recovered from the condition, but with lasting effect due to a disease, injury, treatment, or procedure. If a sequela meets an SAE criterion, the AE must be reported as an SAE.
- Not recovered/not resolved: The condition of the patient has not improved and the symptoms are unchanged, or the outcome is not known.
- Fatal: This term is only applicable if the patient died from a condition related to the reported AE. Outcomes of other reported AEs in a patient before he/she died should be assessed as "recovered/resolved," "recovering/resolving," "recovered/resolved with sequelae," or "not recovered/not resolved." An AE with a fatal outcome must be reported as an SAE.
- Unknown: This term is only applicable if the patient is lost to follow-up.

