10.2 Serious Adverse Events

An SAE is any untoward medical occurrence that at any dose:

- Results in death
- Is life-threatening
- Requires inpatient hospitalization or prolongation of existing hospitalization
- Results in persistent or significant disability or incapacity
- Is a congenital anomaly or birth defect
- Medically important

Medical judgement must be exercised in deciding whether an AE is believed to be "medically important." Medically important events may not be immediately life-threatening or result in death or hospitalization, but may jeopardize the patient or may require intervention to prevent 1 of the other outcomes listed in the definition above.

Suspected Unexpected Serious Adverse Reactions (SUSAR)

A SUSAR is an AE fulfilling 1 of the criteria of seriousness and being assessed as related to an IMP, the nature or severity of which is not consistent with the applicable reference document (e.g., ZP4207 IB or package leaflet/SPC for an approved product).

Clinical Trial Protocol
ZP4207-16051

Version number: 8.0
Amendment 7.0
Date: 06 January 2017

Unanticipated Adverse Device Effect (UADE)

A UADE is any serious adverse effect on health or safety, any life-threatening problem or death caused by, or associated with a device, if that effect, problem, or death was not previously identified in nature, severity, or degree of incidence in the application; or any other unanticipated serious problem associated with a device that relates to the rights, safety, or welfare of patients.

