The Investigator must report initial information in writing on the SAE Form for all SAEs to the Sponsor's responsible pharmacovigilance unit (here: Lindeq) immediately (within 24 hours) after obtaining knowledge about the event.

Name: [REDACTED]
Company: Lindeq
Address: [name]
Tel: [REDACTED]
Fax: [REDACTED]
Mobile: [REDACTED]
E-mail: [contact]

In addition and meeting the same timeline, Investigators must report all SAEs to Zealand Pharma A/S by forwarding the SAE Form electronically within 24 hours of obtaining knowledge of the event to the representatives of Zealand Pharma A/S.

Names: [REDACTED] and [REDACTED]
Address: [name]
Tel: [REDACTED]
E-mails: [REDACTED]

It is the responsibility of Lindeq to report all SUSARs that occur in this trial to the Competent Authorities and to the Investigators. It is the responsibility of the Investigators to report the SUSARs to the IRBs in accordance with the local requirements in force and the International Conference on Harmonisation (ICH) guideline for Good Clinical Practice (GCP). The trial monitor must be informed accordingly.

It is the responsibility of Lindeq to report all serious adverse reactions on insulin lispro and glucagon for injection to the Eli Lilly Pharmacovigilance department within 5 days.

It is the responsibility of the Investigators to report all UADEs to Beta Bionics within 24 hours of the time they are detected. It is the responsibility of the Investigators to report all UADEs to the IRB in accordance with the local requirements in force and the ICH GCP. It is the responsibility of Beta Bionics to report all UADEs to the Competent Authorities.

All device deficiencies should be documented and should be reported to Beta Bionics within 24 hours. Device deficiencies are inadequacies of a medical device with respect to its identity, quality, durability, reliability, safety, or performance.

Name: [REDACTED]
Company: Beta Bionics, Inc.
Address: [name]
[name], United States
Tel: [REDACTED]
E-mail: [REDACTED]

Clinical Trial Protocol
ZP4207-16051

Version number: 8.0
Amendment 7.0
Date: 06 January 2017

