10.6 Safety Monitoring

10.6.1 Data and Safety Monitoring Board

An external DSMB will oversee the conduct of the trial, as set forth in the DSMB Charter. Additionally, the DSMB will be informed in the event of any serious and unexpected AEs. The DSMB will be informed if there are any changes to the trial protocol that could significantly impact the safety or scientific validity of the trial. A final DSMB meeting will convene after the completion of the trial.

The participation of individual patients will be discontinued if they experience:

- Seizure or unconsciousness associated with hypoglycemia and associated with participation in the trial
- Persistent nausea and vomiting thought to be related to glucagon dosing associated with participation in the trial
- Hospitalization associated with participation in the trial
- Pregnancy
- Diabetic ketoacidosis

If more than 1 patient must be withdrawn from the trial for these reasons, the trial will stop and a vote of the DSMB will be required to restart it. All AEs that are serious and unexpected but related will be reported to the DSMB within 5 working days.

Note that patients may discontinue participation at any time. Patients may be removed from the trial for other reasons, for instance, failure to comply with trial procedures or intercurrent illness that is unrelated to the BP but that precludes safe participation. Discontinuation of participation for these reasons will not contribute to a decision to discontinue the trial.

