11.2.1 Analysis of Safety

The following variables will be evaluated according to treatment for safety purposes:

Adverse Events

All AEs will be coded using the latest version of Medical Dictionary for Regulatory Activities (MedDRA). Individual AEs will be presented in a listing including relationship to trial product/device, severity, and treatment period at onset. If more than 20 treatment-emergent AEs (AEs with onset after [first] dosing at Visit 3 until the Follow-up Visit 6) are registered, a summary table including number of AEs, number of patients with at least 1 AE, and percentage

Clinical Trial Protocol
ZP4207-16051

Version number: 8.0
Amendment 7.0
Date: 06 January 2017

of exposed patients with at least 1 AE will be made by system organ class and treatment period at onset.

Local Tolerability

Local tolerability at the injection site will be summarized using descriptive statistics as appropriate.

Laboratory Safety Assessments

Laboratory assessments will be summarized. A listing of abnormal values will be provided.

Physical Examination

A frequency table will show the number and percentage of physical examination results.

Vital Signs

Vital signs will be summarized using descriptive statistics.

12-lead ECG

The Investigator's evaluations of 12-lead ECGs will be summarized and abnormal individual evaluations will be listed together with the Investigator's comments. Changes in 12-lead ECG between measurements will be recorded as AEs if the Investigator judges them to be clinically significant.

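### Section 10.1.3 has no place for a suspected but under-documented drug reaction except 'not related', so such a serious unexpected event can miss SUSAR and 5-day DSMB reporting

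*Protocol*

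**What the plan says.** Section 10.1.3 of the current protocol (version 8.0, Amendment 7.0) names the assessor and the scale: "The causality of each AE should be assessed by the Investigator according to the following classification". Two levels follow: "Related: Good reason and sufficient documentation to assume a causal relationship" and "Not related: No relationship to trial product can be established". There is no intermediate grade and no statement of how a doubtful case is to be scored.

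Section 10.3 has causality recorded separately for ZP4207, insulin, glucagon, the device and the procedures.

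The result is used in three places:

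- Section 10.2: "A SUSAR is an AE fulfilling 1 of the criteria of seriousness and being assessed as related to an IMP", with the further condition that it is not consistent with the reference document. Section 10.3 attaches the onward duty: "It is the responsibility of Lindeq to report all SUSARs that occur in this trial to the Competent Authorities and to the Investigators".
- Sections 4.4 and 10.6.1: "All AEs that are serious and unexpected but related will be reported to the DSMB within 5 working days".
- Section 11.2.1: "Individual AEs will be presented in a listing including relationship to trial product/device, severity, and treatment period at onset".

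**The concern.** The two definitions are not mirror images. Related sets a positive test with two parts, reason and documentation. Not related does not ask that a link be excluded, only that none could be established. The ordinary bedside case, where a reaction is suspected but other explanations remain, falls on the not-related side.

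That case is likely here. ZP4207 or glucagon is delivered alongside insulin from the bionic pancreas, a raised basal rate from the patient's own pump, a meal bolus and structured exercise (section 7.4.1). With several candidate causes, sufficient documentation for any single one is hard to assemble. Section 1.5 also expects that new and unknown side effects may occur, and these are the least documented when first seen.

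At stake is the speed with which a serious, unexpected, suspected reaction reaches the authorities and the DSMB, and how far the relationship column of the AE listing can be trusted. Safety is the primary objective of the trial.

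**Working it through.** No arithmetic applies. The protocol states no figure for related events, so the check is to sort the possible cases by the two definitions and then follow the score to each place where it acts as a condition.

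**Step 1: sort the cases (section 10.1.3).**

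| Reason to suspect a link | Documentation | Meets Related? | Score as written |
|---|---|---|---|
| Good | Sufficient | Yes | Related |
| Good | Insufficient | No, second part fails | Not related, because no relationship has been established |
| None | Any | No, first part fails | Not related |

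The second row is the problem. Suspected events share a score with events that have no apparent link.

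**Step 2: look for an override.** Sections 10.1 to 10.6 contain no instruction to count doubt as related, no possible grade, and no provision for the sponsor to raise the investigator's causality score. The only causality scale defined is the one in 10.1.3.

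**Step 3: follow a second-row event that is serious and unexpected.**

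| Route | Depends on Related? | Outcome |
|---|---|---|
| SAE form to the pharmacovigilance unit and sponsor within 24 hours (10.3) | No | Reported |
| SUSAR status, then authorities and investigators (10.2, 10.3) | Yes | Missed |
| DSMB report within 5 working days (4.4, 10.6.1) | Yes | Missed |
| General DSMB notice (10.6.1) | No | Reported, with no time limit stated |
| Relationship column of the AE listing (11.2.1) | Yes | Shown as not related |
| Number and type of AEs (8.1) and AE summary table (11.2.1) | No | Counted |

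**Step 4: compare with thresholds elsewhere in the protocol.** For a UADE, section 10.2 accepts an effect merely associated with the device. For withdrawal because of persistent nausea and vomiting, section 4.4 asks only that it be thought related to glucagon dosing. The S in SUSAR stands for suspected, yet under 10.1.3 a suspicion without sufficient documentation cannot qualify. The causality scale for the drugs is the stricter one.

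**The case against.** The best defence is that the text asks for reason and documentation to assume causality, not to prove it. An investigator could treat close timing, recorded dosing and known pharmacology as sufficient; section 1.5 already names nausea and low blood pressure as effects seen at higher doses. This has force. The wording does not compel not related in every doubtful case, and a sensible investigator may score some of them related. But the documentation requirement remains, the doubtful case still has no stated category, and two investigators could reasonably differ.

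The second defence is the set of safeguards that ignore causality. All SAEs reach the sponsor within 24 hours. Section 10.6.1 says "the DSMB will be informed in the event of any serious and unexpected AEs". The sponsor's Safety Committee has a planned review of all AEs (section 10.6.2). These stand, and they rule out any claim that such an event would go unseen. They do not supply the onward SUSAR report or the 5-day limit.

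A reader might infer that the rule makes ZP4207 look better tolerated than it is, or that events drop out of the primary endpoint. The documents do not support this. The AE component of section 8.1 and the summary table in 11.2.1 count events whatever their cause, and section 11.2.1 plans no table of related AEs. Nausea and pain VAS and Draize scores are collected hourly, and vital signs at visit start and end, without a causality call. The same definitions apply to Lilly glucagon, also an IMP under 10.1.3, so nothing here shows a bias between treatments.

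**Conclusion.** The point holds as a gap in the causality definitions that affects safety reporting. Under section 10.1.3 as written, a suspected but insufficiently documented reaction is scored not related; if it is serious and unexpected, it can miss both the SUSAR route and the 5-working-day DSMB report. The relationship column of the AE listing carries the same understatement for both ZP4207 and Lilly glucagon. That column matters most if no more than 20 treatment-emergent AEs are registered, because section 11.2.1 then requires no AE summary table.

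The size cannot be stated. The protocol gives neither an expected number of AEs nor the share that would be doubtful at the bedside, so any count of misclassified events would only restate an assumption. The conclusion rests on two premises: that the definitions are applied literally, and that the relatedness conditions in 10.2, 4.4 and 10.6.1 refer to the 10.1.3 assessment, the only one the protocol defines. It does not extend to the primary endpoint counts or to the comparison between treatments.

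**What to change.** Reword section 10.1.3 so that the two levels are complementary:

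- *Related: there is a reasonable possibility of a causal relationship.*
- *Not related: there is no reasonable possibility of a causal relationship.*

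Every event then has exactly one score for each item assessed. Avoid a rule based on whether a relationship can be ruled out. With several agents acting on the same day, little can be ruled out and the flag would stop discriminating.

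State that the definitions apply to each of the five relationship items in section 10.3, and that this assessment governs SUSAR classification in 10.2 and the DSMB report in 4.4 and 10.6.1.

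The cost is two reworded definitions, one added sentence, and matching eCRF instructions. Design, sample size and treatment are untouched. The downside is that somewhat more events will be flagged related, sometimes to more than one agent.

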10.2 Serious Adverse Events

An SAE is any untoward medical occurrence that at any dose:

- Results in death
- Is life-threatening
- Requires inpatient hospitalization or prolongation of existing hospitalization
- Results in persistent or significant disability or incapacity
- Is a congenital anomaly or birth defect
- Medically important

Medical judgement must be exercised in deciding whether an AE is believed to be "medically important." Medically important events may not be immediately life-threatening or result in death or hospitalization, but may jeopardize the patient or may require intervention to prevent 1 of the other outcomes listed in the definition above.

Suspected Unexpected Serious Adverse Reactions (SUSAR)

A SUSAR is an AE fulfilling 1 of the criteria of seriousness and being assessed as related to an IMP, the nature or severity of which is not consistent with the applicable reference document (e.g., ZP4207 IB or package leaflet/SPC for an approved product).

Clinical Trial Protocol
ZP4207-16051

Version number: 8.0
Amendment 7.0
Date: 06 January 2017

Unanticipated Adverse Device Effect (UADE)

A UADE is any serious adverse effect on health or safety, any life-threatening problem or death caused by, or associated with a device, if that effect, problem, or death was not previously identified in nature, severity, or degree of incidence in the application; or any other unanticipated serious problem associated with a device that relates to the rights, safety, or welfare of patients.

